#### **2.4.5 Analyses of safety data**

The summary of safety results will be presented by treatment group.

##### ***General common rules***

All safety analyses will be performed on the safety population as defined in [Section 2.3.2](#), unless otherwise specified.

The analysis of the safety variables will be essentially descriptive and no systematic testing is planned. Relative risks versus placebo and their 95% confidence intervals (CIs) may be provided, if relevant.

##### **2.4.5.1 Analyses of adverse events**

###### ***Generalities***

The primary focus of adverse event reporting will be on treatment-emergent adverse events. Pre-treatment and post-treatment adverse events will be described separately.

If an adverse event date of onset (occurrence or becoming serious) is incomplete, an imputation algorithm will be used to classify the adverse event as pre-treatment, treatment-emergent, or post-treatment. The algorithm for imputing the treatment emergent status will be conservative and will classify an adverse event as treatment emergent unless there is definitive information to determine it is pre-treatment or post-treatment. Details on classification of adverse events with missing or partial onset dates are provided in [Section 2.5.3](#).

Regarding treatment discontinuation, following definitions will be used:

- **Premature** treatment discontinuation is defined as the discontinuation of at least one of the study drugs but at least one is continued.
- **Definitive** treatment discontinuation is defined as the discontinuation of all the study drugs.

The severity grade will be taken into account in the summary. For patients with multiple occurrences of the same adverse event, the maximum (worst) grade by period of observation is used. Summaries will be provided for all grades and for Grade  $\geq 3$  (including Grade 5). Missing grades, if any, will be included in the “all grades” category.

Sorting within tables ensures the same presentation for the set of all adverse events within the observation period (pre-treatment, treatment-emergent and post-treatment). For that purpose, the table of all treatment-emergent adverse events presented by SOC and PT sorted by the internationally agreed SOC order (see [Appendix B](#)) and decreasing frequency of PTs within SOCs will define the presentation order for all other tables unless otherwise specified. Sorting will be based on results for the IPd arm.

The AE incidence tables presented by primary SOC, HLGT, HLT and PT will present the number (n) and percentage (%) of patients experiencing an AE sorted by SOC internationally agreed order, then by alphabetic order of HLGT, HLT and PT.

### ***Analysis of all treatment-emergent adverse events***

The following TEAE summaries will be generated for the safety population.

- Overview of TEAEs, summarizing number (%) of patients with any
  - TEAE any grade, regardless of relationship,
  - TEAE of Grade  $\geq 3$ ,
  - TEAE of Grade 3-4,
  - TEAE with Grade 5 (any TEAE with fatal outcome during the treatment period),
  - Serious TEAE,
  - Serious treatment-related TEAE,
  - TEAE leading to definitive (full study treatment) discontinuation,
  - TEAE leading to premature discontinuation of isatuximab,
  - TEAE leading to premature discontinuation of dexamethasone,
  - TEAE leading to premature discontinuation of pomalidomide,
  - AESI: IRs of Grade  $\geq 3$ ; pregnancy, overdose and second primary malignancy, if any, will be presented separately,
  - Treatment-related TEAEs,
  - Treatment-related TEAEs of Grade  $\geq 3$ .

Treatment-related TEAEs are TEAEs related to at least one drug of the combination.

Analysis of adverse events will be performed according to following domains:

- TEAEs (regardless relationship to study treatment)
- Drug related TEAEs

- Deaths, serious adverse events, adverse events leading to withdrawal (premature or definitive), and other significant adverse events (IR and IR symptoms, Selected respiratory TEAEs, Specific hematological analysis, Second primary malignancies, TEAE leading to dose modification, pre- and post-treatment AE)

The following frequency distributions of TEAEs (incidence tables) will be provided for the safety population, for all grades combined and Grade  $\geq 3$ :

- All TEAEs by primary SOC, HLGT, HLT and PT, showing number (%) of patients with at least 1 TEAE sorted by the SOC internationally agreed order. The other levels (HLGT, HLT, PT) will be presented in alphabetical order.
- All TEAEs by primary SOC and PT, showing the number (%) of patients with at least 1 TEAE, sorted by the internationally agreed SOC order and by decreasing incidence of PTs within each SOC. This sorting order will be applied to all other tables, unless otherwise specified.
- Most frequent ( $\geq 5\%$  of patients in any group) treatment emergent adverse events by primary SOC and PT.
- Most frequent ( $\geq 5\%$  of patients in any group) treatment emergent adverse events by PT.
- All related TEAEs by primary SOC and PT, showing the number (%) of patients with at least 1 related TEAE, sorted by the sorting order defined above.

#### ***Analysis of all serious treatment emergent adverse event(s)***

- All serious TEAEs by primary SOC, HLGT, HLT and PT, showing number (%) of patients with at least 1 serious TEAE sorted by the SOC internationally agreed order. The other levels (HLGT, HLT, PT) will be presented in alphabetical order.
- All serious TEAEs by primary SOC and PT, showing the number (%) of patients with at least 1 TEAE, sorted by the internationally agreed SOC order and by decreasing incidence of PTs within each SOC.
- Most frequent ( $\geq 2\%$  of patients in any group) serious TEAEs by primary SOC and PT.
- All serious TEAEs related to treatment, by primary SOC and PT, showing the number (%) of patients with at least 1 serious TEAE, sorted by the internationally agreed SOC order.

#### ***Analysis of all treatment-emergent adverse event(s) leading to treatment discontinuation***

- All TEAEs leading to treatment definitive discontinuation by primary SOC, HLGT, HLT and PT, showing the number (%) of patients sorted by the internationally agreed SOC order. The other levels (HLGT, HLT, PT) will be presented in alphabetical order.
- All TEAE leading to treatment definitive discontinuation by primary SOC and PT, showing the number (%) of patients with at least 1 TEAE, sorted by the internationally agreed SOC order and decreasing frequency of PT.
- All TEAEs leading to premature treatment discontinuation of isatuximab, by primary SOC, HLGT, HLT, and PT, showing the number (%) of patients sorted by the internationally agreed SOC order. The other levels (HLGT, HLT, PT) will be presented in

alphabetical order. Summary by primary SOC and PT will also be presented, sorted by the internationally agreed SOC order and decreasing incidence of PT.

- All TEAEs leading to premature treatment discontinuation of pomalidomide, by primary SOC, HLG, HLT and PT, showing the number (%) of patients sorted by the internationally agreed SOC order. The other levels (HLG, HLT, PT) will be presented in alphabetical order. Summary by primary SOC and PT will also be presented, sorted by the internationally agreed SOC order and decreasing incidence of PT.
- All TEAEs leading to premature treatment discontinuation of dexamethasone, by primary SOC, HLG, HLT, and PT, showing the number (%) of patients sorted by the internationally agreed SOC order. The other levels (HLG, HLT, PT) will be presented in alphabetical order. Summary by primary SOC and PT will also be presented, sorted by the internationally agreed SOC order and decreasing incidence of PT.

### ***Analysis of all treatment-emergent adverse event(s) leading to dose modification***

The following summary tables are based on the investigator's intent reported in the AE page ("action taken"):

- All TEAEs leading to dose reduction of any drug by primary SOC and PT, showing the number (%) of patients, sorted by the sorting order defined above.
- All TEAEs leading to dose reduction of isatuximab by primary SOC and PT, showing the number (%) of patients, sorted by the sorting order defined above.
- All TEAEs leading to dose reduction of pomalidomide by primary SOC and PT, showing the number (%) of patients, sorted by the sorting order defined above.
- All TEAEs leading to dose reduction of dexamethasone by primary SOC and PT, showing the number (%) of patients, sorted by the sorting order defined above.
- All TEAEs leading to dose interruption of isatuximab by primary SOC and PT, showing the number (%) of patients, sorted by the sorting order defined above.
- All TEAEs leading to any dose delay of any drug by primary SOC and PT, showing the number (%) of patients, sorted by the sorting order defined above.
- All TEAEs leading to any dose delay of isatuximab by primary SOC and PT, showing the number (%) of patients, sorted by the sorting order defined above.
- All TEAEs leading to dose delay of pomalidomide by primary SOC and PT, showing the number (%) of patients, sorted by the sorting order defined above.
- All TEAEs leading to dose delay of dexamethasone by primary SOC and PT, showing the number (%) of patients, sorted by the sorting order defined above.

Of note as per eCRF completion guideline, action taken of TEAEs leading to dose omissions were to be reported as dose reduction in the AE page of the eCRF.

### ***Analysis of adverse events of special interest***

Number (%) of patients with at least one AESI cited in [Section 2.1.4.1](#) sorted by decreasing incidence of PT (presented separately for each category of AESI).

### ***Analysis of infusion reactions***

The following summaries will be provided:

- Number (%) of patients experiencing IRs according to investigator reported AEs presented by primary SOC and PT (both sorted by decreasing order of frequency) will be summarized by grades (all grades and by grade).
- Description of the IRs (according to investigator reporting):
  - Number (%) of patients by action taken with isatuximab,
  - Number (%) of patients with only 1,  $\geq 1$ ,  $\geq 2$ ,  $\geq 3$ ,  $\geq 4$  and  $\geq 5$  episodes,
  - Number (%) of patients with first occurrence of IR at the first infusion and subsequent infusions,
  - Number (%) of patients with IR at the first and subsequent infusions,
  - Number (%) of patients with at least two episodes of IRs at the same infusion,
  - Day of onset from the isatuximab infusion,
  - Duration (in days).
- Number (%) of patients experiencing TEAEs (related and regardless of causality) within 24 hours from the start of any isatuximab infusion presented by primary SOC and PT (both sorted by decreasing order of frequency) will be summarized by grades (all grades and Grades  $\geq 3$ ).
- Similar tables including all TEAEs within 24 hours from the start of any isatuximab infusion from the selected CMQ (see [Section 2.1.4.1](#)) will also be performed.
- Number (%) of patients experiencing TEAEs (related and regardless of causality), (not only limited to those occurring within 24h of each isatuximab administration) from the selected CMQ (see [Section 2.1.4.1](#)) presented by primary SOC and PT (both sorted by decreasing order of frequency) will be summarized by treatment groups and by grades (all grades and Grades  $\geq 3$ ).
- Number of patients with symptoms of IRs presented by primary SOC and PT (both sorted by decreasing order of frequency) will be summarized by grades (all grades and Grades  $\geq 3$ ).

### ***Second primary malignancies***

A listing of patients who reported second primary malignancies during the study will be provided (as per the CMQ). This listing will include diagnosis, study day of diagnosis (from first dose), number of days from last study treatment to diagnosis, prior exposure to anti-myeloma treatments, and whether or not patient received subsequent anti-cancer treatment.

In addition, treatment-emergent and post-treatment AEs in the CMQ 'Second primary malignancies' will be presented by sub-category ('haematological', 'non-hematological skin tumors', 'non-hematological non-skin tumors' and 'other tumors') and by decreasing incidence of PT.

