ASSESSMENT SCHEDULE	
The following evaluations will be performed at baseline only:
 
• Demographic characteristics and medical history• Prior multiple myeloma history (diagnosis, stage at diagnosis and at study entry, prior anti multiple myeloma therapies)• Molecular analysis on blood (immune genetic determinant) and bone marrow samples (FISH for high risk cytogenetic and MRD)• Complete blood phenotyping including information of cross-matching and antibody screening if not yet available (local laboratory) (IPd arm only) 
Safety evaluation will be performed continuously throughout the study period and will include the following:
 
• Vital signs and physical exam• Adverse event evaluation. Severity grade will be determined according to the NCI CTCAE v4.03• Laboratory tests in blood and urine, including pregnancy tests (urine or serum; with a minimum sensitivity of 25 mIU/mL) prior to each cycle in females with childbearing potential (local laboratory)• ECOG PS• Cytokines (tumor necrosis factor alpha (TNF-α), IL-1-β, interleukines (IL) IL-4, IL-6 and interferon gamma (IFN)), markers of complement activation (C3a, C4, CH50), serum tryptase in the IPd arm (central laboratory)• Tumor Lysis Syndrome (TLS) markers (uric acid, creatinine, potassium, phosphate, calcium and corrected calcium) if needed (local laboratory)• Level of human anti-drug antibodies (ADA) in the IPd arm (central laboratory)• Second primary malignancies during and any time after treatment until the end of the study 
The following disease assessment procedures will be performed at screening (for eligibility) and again at Cycle 1 Day 1 prior to study treatment administration (baseline for response assessment) and then Day 1 of every cycle during treatment up to progression and for patients who discontinue study treatment for reasons other than progression, every 4 weeks during follow-up until PD (even for patients who would initiate further anti-myeloma therapy without PD):
 
• M-protein quantification (serum and 24-hour urine, protein immunoelectrophoresis and immunofixation) (local and central laboratory)• Free light chains quantification (local and central laboratory)• Quantitative immunoglobulins (local and central laboratory) 
Other examinations for disease assessment will be done as below:
 
• Bone marrow aspiration (or biopsy as clinically indicated) at baseline, and then to confirm response or progression as clinically indicated (local laboratory for plasma cells involvement, and in case of CR central laboratory will be done to assess MRD)

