
DURATION OF STUDY PERIOD (per patient)
	
The duration of the study for a patient will include a period for screening of up to 21 days (or up to 28 days for FCBP). The cycle duration is 28 days.
 
Patients will continue study treatment until disease progression, unacceptable AEs, patient wish, or any other reason.
 
After study treatment discontinuation, patients will return to the study site 30 days after the last dose of study treatment for EOT assessments, and 60 days after the last dose of study treatment for assessments including ADA (IPd arm only). If ADA test at Day 60 is positive or inconclusive, ADA testing will be repeated every 30 days until negative. If isatuximab is stopped prior to pomalidomide and dexamethasone, ADA will be tested on D1 of the 2 next cycles. If ADA test at the second cycle administered without isatuximab is positive or inconclusive, ADA testing will be repeated every cycle until negative.
 
During follow-up (FU), patients who discontinue the study treatment due to PD will be followed every 3 months (12 weeks) for further anti-myeloma therapy, second primary malignancies, and survival until death or OS cut-off date, whichever comes first. Patients who discontinue the study treatment prior to documentation of PD will be followed-up monthly until confirmation of PD (even for patients who would initiate further anti-myeloma therapy without PD), and then after confirmation of disease progression, every 3 months (12 weeks) for further anti-myeloma therapy, second primary malignancies, and survival, until death or OS cut-off date, whichever comes first.
 
Cut-off date for PFS analysis will be the date when the 162 PFS events have occurred.
 
Cut-off date for OS will be the date when 220 deaths have occurred.
 
If a patient is still on treatment at the time of the cut-off date for OS and benefitting from the study treatment, the patient can continue the study treatment until disease progression, unacceptable AEs, patient wish, or any other reason. For cycles completed after the cut-off date, study

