6.2 DURATION OF STUDY PARTICIPATION

6.2.1 Duration of study participation for each patient

The patient will be considered in the study from informed consent signature until death consent withdrawal, or final OS cut-off date, whichever occurs first.

The duration of the study for a patient will include a period for screening of up to 21 days (or up to 28 days for FCBP). A cycle duration is 28 days. Patients will continue study treatment until disease progression, unacceptable AEs, patient wish, or any other reason. All adverse events occurring after informed consent signature will be reported up to 30 days after last study treatment administration.

After study treatment discontinuation, patients will return to the study site 30 days after the last dose of study treatments for end-of-treatment assessments, and 60 days after the last dose of study treatments for assessments including ADA (IPd arm only). If the ADA test at Day 60 is positive or inconclusive, ADA testing will be repeated every 30 days until negative (IPd arm only). If isatuximab is stopped prior to pomalidomide and dexamethasone, ADA will be tested on Day 1 of the 2 next cycles. If the ADA test at the second cycle administered without isatuximab is positive or inconclusive, ADA testing will be repeated every cycle until negative.

The related AEs and all SAEs regardless of relationship to study treatment ongoing at the time of study treatment discontinuation will be followed during the follow-up period until resolution or stabilization. During the follow-up period, any new related adverse events (regardless of seriousness) will be collected and followed until resolution or stabilization.

During FU, patients who discontinue study treatment due to progressive disease (PD) will be followed every 3 months (12 weeks) for further anti-myeloma therapy, second primary malignancies, and survival until death or final OS cut-off date, whichever comes first. Patients who discontinue the study treatment prior to documentation of PD will be followed-up monthly until confirmation of PD (even for patients who would initiate further anti-myeloma therapy without PD), and then every 3 months (12 weeks) for further anti-myeloma therapy, second primary malignancies, and survival, until death or final OS cut-off date, whichever comes first.

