11.4.3.4 Other safety evaluations

Laboratory data

Clinical laboratory values will be analyzed after conversion into standard international units. International units will be used in all listings and tables. Complete blood count and serum chemistry results will be graded according to NCI-CTCAE Version 4.03, when applicable. For patients with multiple occurrences of the same laboratory variable during the TEAE period, the maximum grade (worst) per patient will be used. The denominator used for percentage calculation is the number of patients with at least 1 evaluation of the laboratory test during the considered observation period.

The number and proportion of patients with abnormal laboratory tests at baseline (ie, last assessment before the first dose of study treatments administration) will be presented for \geq Grade 3, all grades together and Grade 3 and Grade 4 separately. Similar tables showing abnormalities during the TEAE period will be provided.

When the NCI-CTCAE V4.03 scale is not applicable, the number of patients with a laboratory abnormality out-of-normal laboratory range value will be displayed.

Vital signs

Potentially clinically significant abnormality (PCSA) values are defined as abnormal values considered medically important by the Sponsor according to predefined criteria/thresholds based on literature review. The incidence of PCSAs prior to study treatment administration at any cycle during the TEAE period (on-treatment PCSAs) will be summarized by treatment group whatever the baseline level and/or according to the following baseline categories:

- Normal/missing.
- Abnormal according to PCSA criterion or criteria.

The incidence of PCSA during and after study treatment administration at any cycle during the TEAE period in the IPd arm will also be summarized.

Other evaluations

Cytokines (TNF- α , IL-1- β , IL-4, IL-6, IFN- γ), markers of complement activation (C3a, C4, CH50), serum tryptase will be summarized with descriptive statistics.

Number (%) of patients with second primary malignancies will be summarized.

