### ***Analysis of pre-treatment and post-treatment adverse events***

- All pre-treatment AEs by primary SOC and PT, showing the number (%) of patients with at least 1 pre-treatment AE, sorted by the internationally agreed SOC order and decreasing incidence of PTs within each SOC.
- All pre-treatment serious adverse events by primary SOC and PT, showing the number (%) of patients with at least 1 pretreatment serious adverse event, sorted by the internationally agreed SOC order and decreasing incidence of PTs within each SOC.
- All post-treatment AEs by primary SOC and PT, showing the number (%) of patients with at least 1 post-treatment AE, sorted by the internationally agreed SOC order and decreasing incidence of PTs within each SOC.
- All post-treatment SAEs by primary SOC and PT, showing the number (%) of patients with at least 1 post-treatment SAE, sorted by the internationally agreed SOC order and decreasing incidence of PTs within each SOC.

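### Second primary malignancies are followed to death or the OS cut-off, but the arms are compared only by crude counts and percentages; no planned malignancy rate uses post-treatment time at risk

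*SAP*

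**What the plan says.** **Follow-up.** Second primary malignancies are an adverse event of special interest (Protocol 10.4.1.3; SAP 2.1.4.1). The assessment schedule in the Clinical Trial Summary lists "Second primary malignancies during and any time after treatment until the end of the study". Protocol 6.2.1 has patients followed every 3 months for "second primary malignancies, and survival until death or final OS cut-off date, whichever comes first".

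**Summaries.**
- Protocol 11.4.3.4: "Number (%) of patients with second primary malignancies will be summarized".
- SAP 2.4.5.1, adverse events of special interest: "Number (%) of patients with at least one AESI cited in" the list that includes these malignancies.
- SAP 2.4.5.1, Second primary malignancies: a listing with diagnosis, study day, days since last treatment, prior therapies and later anti-cancer therapy; then "In addition, treatment-emergent and post-treatment AEs in the CMQ" by sub-category and decreasing incidence of preferred term.
- SAP 2.4.5.1, pre- and post-treatment adverse events: "All post-treatment AEs by primary SOC and PT, showing the number (%) of patients with at least 1 post-treatment AE".

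SAP Table 10 schedules the other significant adverse events, which include second malignancies, again at the second interim and final OS analyses.

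**Patient-year rates.** SAP 2.4.5.1, Exposure-adjusted analyses of TEAEs, gives rates by SOC and preferred term for selected categories: frequent TEAEs, serious TEAEs, TEAEs leading to definitive discontinuation, and fatal AEs outside disease progression. A patient without the event contributes the length of the treatment period, which SAP 2.1.4 ends 30 days after the last dose. The cumulative patient-years in SAP 2.4.3.1 are drug exposure.

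**The concern.** A percentage of patients with a second malignancy reflects both the underlying rate and how long patients were alive and observed. If IPd prolongs survival, equal rates produce a somewhat higher IPd percentage over full follow-up, and a reader could take that as a drug effect. If IPd delays progression with a smaller survival gain than planned, IPd patients may spend less time in the post-treatment period, and a post-treatment table could then flatter IPd. The plan offers no malignancy rate over the same window as the follow-up, so its tables do not show which part of a difference is only time. With a handful of cases, a difference of one or two is easy to misread in either direction.

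**Working it through.** **1. Reproducing the design.** The documents state no malignancy rate or person-time, so only the design inputs can be checked.
- PFS events (Schoenfeld, hazard ratio 0.60, one-sided 0.025, 90% power): 4 × (1.960 + 1.282)² / (ln 0.60)² = 161.1, giving 162 as stated.
- OS power with 220 deaths at hazard ratio 0.685, ignoring interim looks: Φ(√220/2 × 0.378 − 1.960) = 80.1%. SAP 1.3 states 80%; the protocol states 79.3% with the interim looks.

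**2. Inputs** (Protocol 11.1): exponential PFS and OS; Pd median OS 13 months; PFS medians 4 and 6.67 months; 150 patients per arm; 15 per month, hence 20 months of uniform accrual; final OS cut-off at 220 deaths. Assumed here: OS hazard ratios other than 0.685, and an equal malignancy rate of 2, 3 or 5 per 100 patient-years in both arms. Time runs from randomization, which is within a few working days of first dose.

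**3. Full follow-up time at risk.** With λ = ln 2/13 = 0.0533 per month in Pd and HR × λ in IPd, and f the time from entry to cut-off, mean time at risk is the average over accrual of (1 − exp(−λf))/λ. The cut-off month solves 150 × (P(death, Pd) + P(death, IPd)) = 220.

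| OS HR | Cut-off month | Pd patient-years | IPd patient-years | IPd/Pd |
|---|---|---|---|---|
| 0.685 | 40.9 | 187.0 | 228.9 | 1.22 |
| 0.758 | 39.3 | 183.0 | 212.2 | 1.16 |
| 0.85 | 37.7 | 178.4 | 194.6 | 1.09 |
| 1 | 35.7 | 171.9 | 171.9 | 1.00 |

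At 198 deaths (second interim) the ratios are 1.19, 1.14, 1.08 and 1.00. The plan projects 220 deaths at about month 51, later than this model gives. Stretching both OS medians by 1.3 puts about 223 deaths at month 51, with 246.5 and 302.5 patient-years at hazard ratio 0.685, a ratio of 1.23. The result is not sensitive to that discrepancy.

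**4. Expected patients with a malignancy at equal rates.** With h the monthly malignancy rate, expected cases are 150 × average of h/(h + λ) × [1 − exp(−(h + λ)f)].

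| Rate per 100 patient-years | HR 0.685: Pd, IPd (excess) | HR 0.758: Pd, IPd (excess) |
|---|---|---|
| 2 | 3.67, 4.48 (0.8) | 3.59, 4.16 (0.6) |
| 3 | 5.46, 6.65 (1.2) | 5.34, 6.18 (0.8) |
| 5 | 8.92, 10.86 (1.9) | 8.75, 10.10 (1.4) |

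At hazard ratio 1 the excess is 0. Treating the counts as independent Poisson at hazard ratio 0.685, IPd has the same number or fewer in 46%, 42% and 37% of trials.

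**5. Split by period.** Assume treatment ends at the PFS event, and set the hazard of ending treatment alive at ln 2/(PFS median) − OS hazard (Pd: 0.1733 − 0.0533 = 0.1200 per month). Add 30 days and truncate at death and cut-off.

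| OS HR | On-treatment patient-years, Pd/IPd | Post-treatment patient-years, Pd/IPd | Post-treatment ratio IPd/Pd |
|---|---|---|---|
| 0.685 | 79.8/121.9 | 107.2/107.0 | 1.00 |
| 0.758 | 79.6/120.4 | 103.4/91.8 | 0.89 |
| 0.85 | 79.4/118.5 | 99.0/76.1 | 0.77 |
| 1 | 78.9/115.6 | 93.0/56.3 | 0.61 |

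The on-treatment ratio is about 1.5 throughout. At hazard ratio 0.685, 57% of Pd time (107.2/187.0) and 47% of IPd time (107.0/228.9) falls after the treatment period. Adding an assumed 4% per month of further early stopping moves the post-treatment ratios to 1.13, 1.03, 0.92 and 0.77.

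**6. Precision of the proposed rate.** The 95% interval for the rate ratio spans a factor of about exp(1.96 × √(1/c₀ + 1/c₁)) each way, where c₀ and c₁ are the expected counts: 3.97, 3.10 and 2.42 at rates 2, 3 and 5 and hazard ratio 0.685.

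**The case against.** The case against is substantial. Safety analysis is essentially descriptive (SAP 2.4.5), the counts and the listing are correct, and the SAP delivers more than the protocol promised. For a rare event, a dated case listing may be the most useful output. Together with the OS numbers at risk in SAP 2.4.4.2, it lets a reader approximate a rate. The rate ratio would have an interval of a factor of 2.4 to 4.0 each way, against a distortion of at most 1.22 over full follow-up. All of that stands, and it limits the weight of the point. It does not supply the missing denominator.

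Three stronger readings are tempting and should be resisted.
- *That second malignancies never enter a patient-year rate.* Serious TEAEs are in the exposure-adjusted analyses, and Protocol 10.4.1.2 lists cancers diagnosed during the study as medically important if judged unusual or significant. Some on-treatment cases will therefore be counted, by SOC and preferred term. A fatal post-treatment case may also enter one numerator, because the fatal-AE category uses the definition in SAP 2.4.5.2, which includes AE deaths more than 30 days after the last dose. The event-free denominator still stops at the treatment period.
- *That the percentages are biased against IPd by a known amount.* The direction and size depend on the OS effect, on treatment duration and on which period a table covers.
- *That the SAP leaves period handling undefined.* The general rule is set: "Pre-treatment and post-treatment adverse events will be described separately". Whether one table pools the periods is table-shell detail.

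**Conclusion.** The gap is real and small. No planned output gives a second-malignancy rate over the follow-up in which these events are collected, while time at risk is expected to differ between arms: a full follow-up ratio of 1.00 to 1.22 for OS hazard ratios from 1 to 0.685, and about 1.5 on treatment if treatment ends at the PFS event. Crude percentages can therefore mislead modestly, by an expected one to two patients at the design OS effect. This rests on the plan's exponential assumptions, on a treatment duration that the documents do not give, and on assumed malignancy rates. Nothing planned is wrong and no decision rule depends on it. It is an optional improvement, worth making because it is cheap and because the sponsor already accepted the principle: SAP version 2 added exposure-adjusted TEAE analyses, with FDA comments among the reasons given.

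**What to change.** In SAP 2.4.5.1, Second primary malignancies, add text such as:

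> The incidence rate of second primary malignancies per 100 patient-years will be given by arm with an exact Poisson 95% CI, overall and by sub-category, on the safety population. Time at risk runs from first dose to first second primary malignancy, death, last contact or cut-off, whichever comes first.

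Produce it at the second interim and final OS analyses, and keep the listing and the percentages.

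The cost is two sentences and one output from dates already collected, with no alpha spent. The downsides should be stated alongside the result: intervals will be wide, the rate assumes a constant hazard, and it mixes time on study treatment with time on later therapy. It should be read as descriptive.
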